9.3.2 Outcomes

9.3.2.1 Primary outcomes

Primary outcome

• First hospitalization for congestive heart failure (HHF) (we will first analyze this by looking at diagnosis code in any position, we will then run the analysis considering diagnosis coding in either the principal or secondary position).

The primary scope of the analysis will be limited to the primary outcome (hospitalization for HF), for which the study will be powered for, and limited to HCRU and cost outcomes. For all exploratory effectiveness outcomes outlined above, we will first examine the number of events, and incidence rate of the events in the follow-up for the unmatched cohort, before performing the final analysis, to evaluate feasibility of inclusion of these exploratory outcomes.

Clinical outcomes will be identified by occurrence of a combination of the ICD 9/10 for the respective condition and HCSPCS code. See additional workbooks "ICD 9 Dx Codes.xlsx" and "ICD 10 Dx Codes.xlsx" and "HCPSC codes.xlsx" for a detailed list of relevant ICD 9/10 codes and HCSPCS codes, respectively.

Effectiveness Outcome	Metformin + Sulfonylurea(IR)	Metformin + Empagliflozin (IR)	Hazard Ratio (95% CI)
HHF			
MACE			
Myocardial infarction			
Stroke			
Coronary revascularization			
All-cause death			

See sample results for the propensity score-matched population below:

Utilization Outcome (12 months post index date)	Metformin + Sulfonylurea (IR)	Metformin + Empagliflozin (IR)	Coefficient (95% CI)	P value
Hospitalizations				
LOS				
ED visits				
Outpatient visits				
Drug orders				
Total care costs				
Medical costs				

Pharmacy costs		
2		

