9.5 STUDY SIZE

The following calculation is intended to estimate the number of events necessary to perform a powered analysis of the effect of add-on treatment with empagliflozin on the incidence of

hospitalization from heart failure. We will use the formula below for the power calculation for a two-group survival analysis:

$$N_e = \frac{(Z_\alpha + Z_\beta)^2}{[\log(HR)]^2 q_0 q_1}$$

where the significance level, α , will be set equal to 5% and the type 2 error threshold, β , will be set equal to 20%, resulting in a Z_{α} and Z_{β} of 0.96 and 0.842, respectively. The EMPA-REG OUTCOME clinical trial reported a hazard ratio of 0.65 (=*HR*), which we have applied in our sample size calculation. Given that there will be substantially more control subjects than treatment subjects and assuming the application of IPTW would have the effect of balancing the cohorts, we consider a range of possible proportions of the control and treatment arms of the study. Below we visualize scenarios with a minimum and maximum proportion of patients in the control arm equal to 0.5 and 0.9, respectively. This corresponds to a minimum and maximum number of events required for a powered analysis of 169 and 470.

Next we must consider the potential incidence rates of hospitalization from heart failure in our study population and the implied number of patients needed in our sample. We note, first, that the EMPA-REG OUTCOME clinical trial reported incidence rates of 14.5 and 9.4 events per 1,000 patient years for the placebo- and empagliflozin-administered arms, respectively. We note, second, that our study population will be at high-risk of cardiovascular events similar to the EMPA-REG OUTCOME study population. Furthermore, using previously referenced evidence of the higher risk of cardiovascular events in sulfonylurea-treated patients we assume that the incidence rate is, at best, equal to that of the placebo-administered population of the EMPA-REG OUTCOME study.

A reasonable scenario might assume that 80% of our patients are in the control arm and use the estimated weighted average of the control and treatment arms $(0.8 \times 14.5 + 0.2 \times 9.4 = 13.48)$ as the incidence rate and 265 events as the necessary number of events. This scenario would require 19,600 patient years available in the dataset.

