Based on preliminary calculation stated below for IQVIA database, we believe there will be a sufficient sample size to conduct a powered analysis of the effect of empagliflozin use compared to either control arm. Nevertheless, the final decision of performing the analysis will

depend on the final sample size and the number of events accrued during the follow-up for primary outcome (*see key study outcomes section for details*)

Metformin Days Supply in PI	Empagliflozin Sample #	Metformin Sample size #		
No Metformin	582	75,563		
0 to 3 months	461	8,771		
3 to 6 months	331	10,409		
6 to 9 months	375	14,275		
9 to 12 months	801	17,029		
Total	2550	126,047		
* The final sample will be different, based on further data cleaning and further application of inclusion/exclusion criteria				

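### Inclusion of MACE and its components is decided from event numbers and rates in the unmatched cohort, not in the cohort where they are compared

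*Protocol*

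**What the plan says.** Section 9.3.2.1 of the protocol limits the primary scope to HHF, resource use and cost. For the exploratory effectiveness outcomes it adds a preliminary step: "we will first examine the number of events, and incidence rate of the events in the follow-up for the unmatched cohort". The step comes before the final analysis, and its stated purpose is to judge whether including these outcomes is feasible. Section 9.3.2.2 names the exploratory outcome as a composite of MI, stroke and coronary revascularization. The results shell in 9.3.2.1 gives the composite and each component a row, with one incidence-rate column per arm.

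The comparison is made elsewhere. Section 9.7.1, Step 3, takes incidence rates from the matched or weighted cohorts, and the Abstract (Data analysis) says the same. The Abstract uses matching only if the matched sample still supports a powered analysis, and weighting (IPTW) otherwise. Section 9.7.1, Step 1, describes 1:1 matching and matching to 2, 3 or 4 controls, and leaves the choice until the dataset has been inspected.

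Section 9.5 has a related condition for the primary outcome: "the final decision of performing the analysis will depend on the final sample size and the number of events accrued during the follow-up".

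**The concern.** Two things are at stake.

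- **The set inspected is not the set analysed.** Under matching, most comparator patients are discarded. An event total that looks ample before matching can be small afterwards, so an outcome could pass the check and then rest on a few dozen events.
- **Inclusion depends on observed outcomes.** The check covers incidence rates as well as counts, and the text does not say that they are pooled over arms. If they are seen by arm, the crude contrast between empagliflozin and sulfonylurea is known before anyone decides whether the outcome enters the report. The condition in 9.5 likewise leaves open that the primary estimate is not produced if events are few.

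Both leave a route to selective reporting in a study whose data already exist and whose outcomes could all be tabulated at little cost.

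**Working it through.** **1. The plan's own event numbers (9.5).** Inputs: "reported a hazard ratio of 0.65", 5% significance, 80% power, and a "minimum and maximum proportion of patients in the control arm equal to 0.5 and 0.9, respectively". The formula is events = (Z_α + Z_β)² / ([ln HR]² q0 q1). With 1.96 and 0.842 the numerator is 7.851, and [ln 0.65]² = 0.1856.

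- q0 q1 = 0.25: 169
- q0 q1 = 0.09: 470

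This reproduces the "minimum and maximum number of events required for a powered analysis of 169 and 470". (The protocol prints Z_α as 0.96; the stated numbers need 1.96.) These figures are for HHF. None is given for MACE.

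**2. Inputs for the illustration.**

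- Patients: the four metformin-exposed rows of the preliminary table in 9.5. Empagliflozin 461 + 331 + 375 + 801 = 1,968. Second column 8,771 + 10,409 + 14,275 + 17,029 = 50,484. That column is headed Metformin, so reading it as the sulfonylurea comparator is an assumption. Its share is 50,484 / 52,452 = 96.2%. The protocol calls the counts provisional.
- Rates: "incidence rates of 14.5 and 9.4 events per 1,000 patient years" for placebo and empagliflozin, which are HHF rates standing in for the missing MACE rates.
- Follow-up: one year per patient (assumed). It cancels in the ratios if equal across arms.

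**3. Event totals.**

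- Empagliflozin, in either set: 1,968 × 9.4/1,000 = 18.5
- Comparator, unmatched: 50,484 × 14.5/1,000 = 732.0, so the total is 750.5
- Comparator, 1:1 with every case matched: 1,968 × 14.5/1,000 = 28.5, so the total is 47.0

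**4. Information on the log hazard ratio**, taken as 1 / (1/d0 + 1/d1), where d0 and d1 are the events per arm.

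- Unmatched: 732.0 × 18.5 / 750.5 = 18.0
- 1:1 matched: 28.5 × 18.5 / 47.0 = 11.2
- Ratio: 1.61

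| Analysis set | Total events | Unmatched/analysed events | Unmatched/analysed information |
|---|---|---|---|
| 1:1 | 47.0 | 16.0 | 1.61 |
| 1:2 | 75.6 | 9.9 | 1.29 |
| 1:3 | 104.1 | 7.2 | 1.19 |
| 1:4 | 132.6 | 5.7 | 1.13 |
| IPTW, full cohort | 750.5 (raw) | about 1 | not computed |

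With 14.5 per 1,000 in both arms, 1:1 matching gives an event ratio of 13.3 and an information ratio of 1.92. With the 9 to 12 month row alone, the 1:1 event ratio is 13.3. Adding the row without metformin, which does not fit the inclusion criteria, makes it 30.4.

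**5. Why a total misleads.** In this illustration 750 lies above the plan's upper figure of 470, while 47 lies below its lower figure of 169. At a 96.2% comparator share, the plan's formula asks for about 1,172 events (q0 q1 = 0.0361), so 750 would fall short even unmatched. The limit is the 18.5 empagliflozin events, which a pooled total hides.

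**The case against.** The best defence has four parts.

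- **The outcomes are exploratory.** They lie outside the primary scope, the stated purpose of the look is feasibility, and they keep rows in the results shell. This stands and limits the weight of the point.
- **A numerical threshold belongs in the analysis plan.** That is a separate milestone and is not shown here. This also stands: the missing threshold is not the finding. What the protocol itself fixes is the cohort and the quantities inspected.
- **A 1:1 analysis on 47 events would probably not happen.** The Abstract moves to IPTW if matching leaves too few events, and then the raw totals agree. This stands for IPTW, but matching is the first choice and the ratio is left open.
- **The two harms do not both arise in full.** A pooled look can mislead on totals but shows no treatment contrast. A look by arm shows the contrast, but also the limiting empagliflozin count. This is fair. The protocol does not say which is meant, and each reading has its own defect.

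Stronger readings are tempting but unsupported. A reader might infer from 750 against 47 that feasibility is overstated 16-fold; that is a ratio of total events, and precision differs much less. A reader might infer that outcomes will be kept or dropped on their direction, and attach an inflated false-positive rate; no such selection rule appears anywhere. A reader might take MACE to be the only other cardiovascular outcome that could temper a favourable HHF result; 9.7.2 plans CVD-related death and the shell in 9.3.2.1 lists all-cause death. Finally, the pointer in 9.5 to a section on key study outcomes matches no section title, but that is a clerical slip.

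**Conclusion.** The point holds in a limited form. Section 9.3.2.1 decides on inclusion from observed outcome data in a cohort that, under matching, is not the one analysed, and it does not exclude crude rates by arm. Total events can be overstated about 6- to 16-fold for 1:4 to 1:1 matching at the stated rates, and about 1-fold under IPTW. Hazard-ratio information is overstated about 1.1- to 1.9-fold under matching. These sizes rest on HHF rates used for MACE, provisional counts, the Metformin column read as comparator, complete matching and equal follow-up. Result-driven selection is something the wording permits, not something it states. The condition in 9.5 has the same weakness for HHF, although it mentions only sample size and event numbers. Because MACE is exploratory, this merits correction but does not threaten the design.

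**What to change.** In 9.3.2.1:

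- Judge feasibility in the matched or weighted cohort, on event counts with treatment labels withheld, against a minimum fixed before the look.
- Report event counts and incidence rates with 95% confidence intervals for MACE and each component whatever the result. Let the minimum decide only whether a hazard ratio is added.

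In 9.5, state that the HHF estimate and its confidence interval will be reported whatever the event count, labelled as under-powered if the target is missed. Correct the cross-reference at the same time.

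The cost is protocol wording and a few extra table rows from data already held. Some reported intervals will be wide.

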Endocrinologist visit within prior 30 days; n (%)		
Endocrinologist visit during prior 31-365 days; n (%)		
No. endocrinologist visits; mean (sd)		
Internal medicine visit within prior 30 days; n (%)		
Internal medicine visit during prior 31-365 days; n (%)		
No. internal medicine visits; mean (sd)		
Cardiologist visit within prior 30 days; n (%)		
Cardiologist visit during prior 31-365 days; n (%)		

No. cardiologist visits; mean (sd)	
Electrocardiogram; n (%)	
No. electrocardiograms, mean (sd)	
No. distinct medication prescriptions; mean (sd)	
Use of glucose test strips; n (%)	
No. HbA1c tests ordered; mean (sd)	
No. glucose tests ordered; mean (sd)	
No. microalbuminuria tests ordered; mean (sd)	
No. creatinine tests ordered; mean (sd)	
No. BUN tests ordered, mean (sd)	
No. lipid tests; mean (sd)	

The table above shows our complete set of baseline characteristics. All comorbidities and previous acute conditions and previous utilization in the previous 12 months will be recorded. Age at index date will be calculated as the time difference between the index date and the patient's birth date. Identification of comorbidities and previous utilization will follow the following rules:

- Chronic comorbidities and previous acute conditions will be identified by occurrence of at least one ICD 9/10 for the respective condition in any position. See the additional workbooks titled "ICD 9 Dx Codes.xlsx" and "ICD 10 Dx Codes.xlsx" for a detailed list of ICD 9/10 codes that identify comorbidities.
- Previous healthcare utilization will be identified by occurrence of CPT or HCPCS codes for the respective form of utilization. See the additional workbooks "CPT codes.xlsx" and "HCSPCS codes.xlsx" for a detailed list of CPT and HCPCS codes.
- Previous prescription medications will be identified by occurrence of prescription filling with a medication's respective NDC or HCSPCS code. See additional workbook "NDC codes.xlsx" and "HCSPCS codes.xlsx" for a detailed list of relevant codes.

Also, given that we are comparing a branded agent against generic agent, we will perform exploratory instrumental variable analysis, in order to account for the confounding by indication. Some example of instrumental variables we can use and will explore the appropriateness of are:

- First three digits of zip code (ZIP3) and/or State
- National Provider Identifier (NPI)
- Index date and/or index quarter

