9.3.2.2 Secondary outcomes

Secondary outcomes

- Healthcare utilization outcomes: hospitalizations, emergency department (ED) visits, length of stay, number of filled drugs, outpatient visits
- All cause cost: Total cost of care, divided by medical (inpatient costs, outpatient costs, emergency costs) and pharmacy costs (all reported in Per Patient Per Month (PPPM) costs)

Exploratory outcomes

• Effectiveness outcomes: 2-point MACE as a Composite Score of myocardial infarction, stroke or coronary revascularization

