9.4 DATA SOURCES

This study will utilize IQVIA's Real-World Data (RWD) Adjudicated Claims Database (formerly known as PharMetrics Plus). IQVIA's claims database is composed of more than 190 million unique enrollees from national and sub-national health plans and self-insured employer groups from 2006 to the present.¹⁵ The database is considered representative of the sex and age demographics of the insured United States population.¹⁶ The database contains a multitude of patient data points that are relevant for this study including:

- Demographic, geographic, and insurance type/enrollment information,
- Primary and specialty care visit dates and diagnosis codes,
- Medication use including refill dates, quantity, and days supplied, and
- Hospitalizations and emergency department visit dates, length of stay, and diagnosis codes

We anticipate having access to claims data that was generated though at least December 31, 2019. IQVIA's database has been extensively used in pharmacoepidemiological research. Recent examples include *Pandya et al.* (2020) and *Stolshek et al.* (2018).^{16,17} The claims data will be fully de-identified prior to receiving access for analyses.

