ANNEX 1. LIST OF STAND-ALONE DOCUMENTS

Documents listed in Annex 1 can be maintained separately from the study protocol. They should be clearly identifiable and provided on request. Write <None> if there is no document or list documents in a table as indicated below.

Number	Document Reference Number	Date	Title
1	<number></number>	<dd mmm="" yyyy=""></dd>	ICD 9 Dx Codes
2	<number></number>	<dd mmm="" yyyy=""></dd>	ICD 9 Proc Codes
3	<number></number>	<dd mmm="" yyyy=""></dd>	ICD 10 Dx Codes
4			ICD 10 Proc Codes
5			CPT Codes
6			HCSPCS Codes
7			NDC Codes

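### The single outcome-coding rule in Protocol 9.3.2.1 leaves out the procedure and CPT lists needed for coronary revascularization and, read literally, conflicts with the HHF definition in the same section

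*Protocol*

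**What the plan says.** Section 9.3.2.1 defines the primary outcome as first hospitalization for congestive heart failure. On coding it says "we will first analyze this by looking at diagnosis code in any position", followed by a second run restricted to the principal or secondary position. No HCPCS condition is attached.

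Later in the same section a general rule covers all clinical outcomes: "Clinical outcomes will be identified by occurrence of a combination of the ICD 9/10 for the respective condition and HCSPCS code". The reader is sent to the two diagnosis workbooks and the HCPCS workbook "for a detailed list of relevant ICD 9/10 codes and HCSPCS codes, respectively". The outcome table that follows has rows for HHF, MACE, myocardial infarction, stroke and coronary revascularization, among others.

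Section 9.3.2.2 gives the exploratory outcome as "2-point MACE as a Composite Score of myocardial infarction, stroke or coronary revascularization".

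Annex 1 lists seven code lists. Item 2 is "ICD 9 Proc Codes", item 4 is "ICD 10 Proc Codes", item 5 is the CPT list and item 6 the HCPCS list. The two ICD procedure lists are cited nowhere in the body of the protocol. CPT is cited only for baseline covariates in 9.3: "Previous healthcare utilization will be identified by occurrence of CPT or HCPCS codes for the respective form of utilization".

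**The concern.** A single rule built on diagnosis and HCPCS codes does not suit all the outcomes it covers.

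- **Coronary revascularization** is a procedure. The lists that record procedures are in Annex 1, but the outcome rule points to only one of the four that could apply.
- **HHF** has a complete definition of its own a few lines earlier. The general rule adds a second condition if taken at its word, so a programmer could build the primary endpoint in two ways.
- **MI and stroke** have no stated care setting. The cohort must have CVD claims in the 12 months before index, and prior MI and stroke are baseline covariates. The rule does not say how a new event is told apart from a follow-up visit for a pre-index one.

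At stake are the completeness of the revascularization and MACE counts, a unique case definition for the primary outcome, and the feasibility check in 9.3.2.1, which decides from observed event counts whether the exploratory outcomes are analysed at all.

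**Working it through.** **1. Which lists reach which variables**

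| Variable | Code source stated | Section |
|---|---|---|
| Baseline comorbidities | at least one ICD-9/10 diagnosis code | 9.3 |
| Baseline utilization | CPT or HCPCS | 9.3 |
| Baseline medications | NDC or HCPCS | 9.3 |
| All clinical outcomes | ICD-9/10 diagnosis in combination with HCPCS | 9.3.2.1 |
| ICD-9/10 procedure lists | not used in the body | Annex 1, items 2 and 4 |

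**2. Revascularization.** The Abstract places previous coronary revascularization under previous healthcare utilization, which 9.3 finds by CPT or HCPCS codes. The same procedure can therefore be found by a CPT code before index but not after it. Section 9.3 names CPT and HCPCS as separate workbooks, and Annex 1 lists them as separate items, so the text gives no ground for assuming that the HCPCS list contains the CPT codes. On the written rule, a revascularization recorded only by an ICD procedure or CPT code is not counted.

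**3. HHF.** There are two readings of the general rule.

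- *Both codes required.* An admission with a listed heart-failure diagnosis but no listed HCPCS code fails the rule, yet meets the HHF definition in the same section. The two statements conflict.
- *Whichever code type applies.* The rule then adds nothing to the HHF definition and there is no conflict.

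The first reading has some textual support, because 9.3 writes *or* where either code suffices and 9.3.2.1 writes *and*. The second has support from the HHF definition itself and from 9.4, which describes hospital records as "Hospitalizations and emergency department visit dates, length of stay, and diagnosis codes". That list in 9.4 is introduced as examples, so it does not show that HCPCS codes are absent from those records.

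**4. What a loss of HHF events would mean, if it occurred.** The protocol's planning case in 9.5 has HR 0.65, 80% of patients in the control arm, 5% significance, 80% power and 265 events. Reproducing it:

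events = (1.96 + 0.842)² / [(ln 0.65)² × 0.8 × 0.2] = 7.851 / (0.18557 × 0.16) = 264.4, rounded up to 265.

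This matches. It needs a Z of 1.96; the 0.96 printed in 9.5 would give 109 events and is a misprint.

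Let s be the share of HHF admissions that carry a listed HCPCS code, equal in both arms. The documents give no value for s, so the values below are assumptions.

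Power = Φ(√(265 × s × 0.16) × 0.43078 − 1.96)

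| s (assumed) | Events kept | Power |
|---|---|---|
| 1.00 | 265 | 80% |
| 0.90 | 238.5 | 76% |
| 0.75 | 198.75 | 68% |
| 0.50 | 132.5 | 51% |

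Incidence rates would fall by the same factor s. The table shows how sensitive the primary analysis would be under the strict reading. It does not estimate a loss. The required event numbers in 9.5 are not affected.

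**The case against.** The strongest reply is that HHF already has a specific definition, that a specific definition overrides a general sentence, and that *combination* may simply mean that codes are drawn from both systems. That stands against any claim that the primary outcome is certainly miscounted. A reader might infer such a claim from the general rule. The documents do not support it, because admissions are lost only if both codes are mandatory, and the text does not settle that. Leaving out the procedure and CPT lists has no effect on diagnosis-based outcomes in itself.

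A reader might also infer that old MI or stroke codes would dilute the hazard ratio from 0.65 towards 1. That is not supported either. The value 0.65 is the planning figure for HHF, which already requires a hospitalization. The protocol states no hazard ratio for MI, stroke or revascularization. The baseline table separates acute from old MI, and stroke from late effects of cerebrovascular disease, so the study's coding does distinguish them. The missing care setting for MI and stroke calls for clarification; it is not a demonstrated bias.

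Two further points carry weight. MACE is exploratory and is analysed only if event counts make it feasible. Code-level logic is also often left to an analysis plan, and the protocol schedules one. The workbooks are not shown, so their contents could narrow the revascularization gap. Against this, the protocol did not leave the matter open: it states a rule and names the lists, and any later document would have to contradict it.

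The two-point label on a three-component composite is an editorial slip. The components are listed consistently and no analysis depends on the label.

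**Conclusion.** The point holds in limited form and should be fixed. For coronary revascularization the stated rule omits the ICD procedure and CPT lists that the protocol already holds, so events recorded only there would be missed. This assumes that the HCPCS workbook does not itself contain the CPT codes, which agrees with the protocol's separate naming of the two. For HHF the finding is an unresolved conflict between two statements in one section. It becomes a loss of events only if both codes are required. The size of either loss cannot be computed from the documents. The consequence is confined to an exploratory composite unless the strict reading is applied to HHF, in which case the primary analysis would lose events and precision.

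**What to change.** In 9.3.2.1, replace the general sentence with a rule for each outcome:

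- **HHF:** a hospitalization after index with a listed ICD-9/10 diagnosis, in the positions already specified; no HCPCS code required.
- **Coronary revascularization:** an ICD-9 or ICD-10 procedure code, or a CPT or HCPCS procedure code, dated after index (Annex 1 items 2, 4, 5 and 6); no diagnosis code required, and none accepted alone.
- **MI and stroke:** an inpatient diagnosis after index, so that follow-up visits for pre-index events are not counted.

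Correct the MACE label to match its three components at the same time. Make these changes before the event counts for the feasibility check are inspected, so that the definitions do not depend on the counts.

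The cost is a few lines of protocol text and the matching code; no new code list is needed. The downside is that some MI or stroke events coded only in outpatient claims are dropped, by a number the documents do not give.
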